### 4 Patient Selection

Study entry is open to those 18 years of age and older regardless of gender, race, or ethnic background. While there will be every effort to seek out and include minority patients, the patient population is expected to be no different than that of other advanced solid tumor studies at the University of Minnesota.

A potential participant must meet all of the inclusion and none of the exclusion criteria to be considered eligible for study participation.

### 4.1 Inclusion Criteria

- **4.1.1** Any histologically or cytologically confirmed advanced/metastatic solid tumor cancer (except pancreatic cancer and primary brain tumor), that has failed at least 2 prior lines of therapy given either in the recurrent or metastatic setting and must be refractory to or intolerant of existing therapy(ies) known to provide clinical benefit for their condition.
- 4.1.2 Measurable disease per RECIST v 1.1. A single target lesion is considered measurable disease provided the lesion meets the definition of measurability as described in RECIST 1.1 (Schwartz 2016). If a target lesion has been surgically removed or treated with radiotherapy, it is not evaluable for response. Although not a requirement for eligibility, patients with tumor assessable may be asked if willing to undergo an optional research related biopsy prior to treatment start and prior to the 3rd treatment course interested participants would provide consent through a separate optional biopsy consent form. Note: If a biopsy is obtained prior to treatment start (any time after consent) and a patient is later deemed ineligible to receive treatment, the tumor sample will not be used for research purposes.
- **4.1.3** Resolved acute effects of any prior therapy to baseline or Grade ≤1 NCI CTCAE v5 except for AEs not constituting a safety risk in the opinion of the enrolling Investigator.
- **4.1.4** Age 18 years or older at the time of consent.
- **4.1.5** ECOG Performance Status 0 or 1. (Refer to Appendix I).
- **4.1.6** Evidence of adequate organ function within 14 days prior to treatment on Cycle 1 Day 1 defined as:
  - hemoglobin ≥9 g/dL (may be transfused not more than 2 units of pRBCs within previous 2 week to meet this requirement)
  - absolute neutrophil count (ANC) ≥1500/ul
  - platelets ≥100 x 10^9/L (may be transfused not more than 1 unit of platelets within previous 2 week to meet this requirement)
  - estimated glomerular filtration rate (eGFR) >40 mL/min or creatinine: ≤1.5 x upper limit of institutional normal (ULN)
  - ALT. AST and ALP ≤ 2.5 x ULN or ≤ 5 x ULN if liver metastases

- **4.1.7** Adequate pulmonary function with PFTs >50% FEV1 if symptomatic or known impairment.
- 4.1.8 Sexually active persons of child-bearing potential or persons with partners of childbearing potential must agree to use (or agree to their partners' use of) a highly effective form of contraception for at least 28 days after the last dose of HCW9218. Non-childbearing is defined as >1 year post-menopausal or surgically sterilized.

Examples of highly effective birth control methods include but are not limited to the following:

- Using twice the normal protection of birth control (i.e., double-barrier) by using a condom AND spermicidal jelly or foam, or a diaphragm AND spermicidal jelly or foam. A spermicidal jelly or foam must be used in addition to a barrier method (e.g., condom or diaphragm).
- Oral contraceptive pills
- Depot or injectable birth control
- Intrauterine Device (IUD)
- Transdermal contraceptive patch
- Vaginal contraceptive ring
- Contraceptive implants

Note: Rhythm method or abstinence alone is not considered to be an adequate method of contraception.

**4.1.9** Provides voluntary written consent prior to the performance of any research related activity.

### 4.2 Exclusion Criteria

- **4.2.1** Pregnant or breastfeeding. Persons of child-bearing potential must have a negative pregnancy test (serum or urine) within 14 days of treatment start.
- **4.2.2** History of clinically significant vascular disease, including any of the following within 6 months prior to start of study treatment: MI or unstable angina, percutaneous coronary intervention, bypass grafting, ventricular arrhythmia requiring medication, stroke or transient ischemic attack, symptomatic peripheral arterial disease.
- 4.2.3 Marked baseline prolongation of QT/QTc interval (e.g., demonstration of a QTc interval ≥470 milliseconds by Fridericia correction). If undiagnosed MI(s) appear on ECG, work up as medically warranted and determine eligibility based on findings. Cardiac function should be monitored by clinical examination and assessment of vital signs for hypotension, arrhythmia, angina, and myocardial infarction during the study period per Section 6.1.1.
- **4.2.4** Known or suspected untreated CNS metastases are excluded. Persons are eligible if CNS metastases are treated and they are neurologically stable for at least 2 weeks prior to enrollment. In addition, must be either off

- corticosteroids, or on a stable or decreasing dose of  $\leq$  10 mg daily prednisone (or equivalent).
- **4.2.5** Anti-cancer treatment including surgery, radiotherapy, chemotherapy, other immunotherapy, or investigational therapy within 14 days before treatment start.
- **4.2.6** Prior malignancy except for the following: adequately treated basal cell or squamous cell skin cancer, in situ cervical cancer, adequately treated Stage I or II cancer currently in complete remission, or any other cancer from which the patient has been disease-free for 3 years after surgical treatment.
- **4.2.7** Known hypersensitivity or history of allergic reactions attributed to compounds of similar chemical or biologic composition to the agents used in the study.
- **4.2.8** Prior therapy with TGF-β antagonist, IL-15 or analogs.
- **4.2.9** Ongoing use of St. John's Wort and/or other herbal CYP modulators as certain cytokines, including IL-2 and TGF-β, have been found to suppress the activities of cytochrome P450 enzymes. The participant may be considered for the study if they discontinued the herbal CYP modulator at least 7 days before the 1st dose of HCW9218 and agree not resume it until after the End of Treatment visit.
- **4.2.10** Known autoimmune disease requiring active treatment. Persons with a condition requiring systemic treatment with either corticosteroids (> 10 mg daily prednisone equivalent) or other immunosuppressive medications within 14 days of enrollment, with the exception of use for persons with CT contrast allergies. Inhaled or topical steroids, and adrenal replacement steroid doses ≤ 10 mg daily prednisone equivalent, are permitted in the absence of active autoimmune disease.
- **4.2.11** Active systemic infection requiring parenteral antibiotic therapy. All prior systemic infections must have resolved following optimal therapy.
- **4.2.12** Prior organ allograft or allogeneic transplantation.
- 4.2.13 Known HIV-positive or AIDS.
- **4.2.14** Psychiatric illness/social situations that would limit compliance with study requirements.
- **4.2.15** Other illness or a medical issue that in the opinion of the Investigator would exclude the subject from participating in this study.

# 5 Patient Screening and Study Enrollment

Written consent must be obtained prior to the performance of any research related tests or procedures.

# 5.1 Consent and Study Screening in UMN OnCore

Any patient who has been consented is to be entered in OnCore by the Study Coordinator or designee. If a patient is consented but is not enrolled in the study treatment, the patient's record is updated in OnCore as a screen failure and reason for exclusion recorded.

# 5.2 Study Enrollment and Treatment Assignment

To be eligible for this study, the patient must sign the treatment consent and meet each inclusion criteria and none of the exclusion criteria listed on the eligibility checklist based on the eligibility assessment documented in the patient's medical record.

If a patient is not starting study treatment within 14 days of baseline eligibility lab work, the blood work in Section 4.1.6 must be repeated within 14 days prior to treatment on Cycle 1 Day 1 to confirm continuing eligibility. If one or more of the lab results do not meet the criteria the patient is taken off study per Section 5.3.

The Study Coordinator or designee updates OnCore with the assigned HCW9218 dose level to complete study enrollment.

# 5.3 Inability to Begin Study Treatment

If a patient is enrolled to the study and is later found not able to begin study treatment, for whatever reason, the patient will be taken off study and treated at the physician's discretion. The Study Coordinator or designee will update OnCore of the patient's non-treatment status. The patient will be replaced to fulfill enrollment requirements and will not be included in the outcome analysis.

### 6 Treatment Plan

#### 6.1 Administration of HCW9218

HCW9218 is given as a subcutaneous (SC) injection at the patient assigned dose once every 3 weeks until disease progression, unacceptable toxicity or continuation of treatment is longer of benefit.

HCW9218 dose calculation is based on patient's assigned dose level and actual body weight recorded at Cycle 1 Day 1 (or within 14 days prior).

This dose is used for the duration of the study treatment unless there is a ±10% or greater change on a subsequent cycle's "Day 1" weight from the weight used to calculate the Cycle 1 Day 1 dose. In this situation, the HCW9218 dose is recalculated using the more recent weight. The new dose is used for subsequent HCW9218 injections, unless a ≥10% weight change occurs based on the newer weight. Depending on the following:

- The 10% weight change is because their weight returned to around their Cycle 1 Day 1 weight – dose may be recalculated and the patient continue HCW9218
- The 10% weight change represents a ≥20% weight change from the Cycle
   1 Day 1 (representing a Grade 3 weight change based on CTCAE v 5)
   meeting the criteria for discontinuing treatment per Section 6.6.

If the total subcutaneous (SC) dose is greater than 1.5 mL, the dose will be divided by IDS into 2-3 SC injections as needed. Injections are given in the abdominal area. The injection site should be rotated per institutional guidelines and each injection site separated by at least 1 inch.

HCW9218 can be administered on an outpatient basis, or if the patient is in the hospital for another reason, as inpatient treatment.

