# Treatment Overview:

Upon signing of consent and confirmation of eligibility, the patient is assigned to the currently enrolling dose level of HCW9218.

HCW9218 at the assigned dose level is administered as a subcutaneous injection once every 3 weeks for a minimum of 2 treatment cycles unless medically contraindicated or participant wishes to discontinue. Patients may continue until disease progression, unacceptable toxicity (an AE meeting the definition of a DLT) or other reason detailed in Section 6.6.

Dosing is initially calculated on the patient's weight taken on Cycle 1 Day 1 or within 14 days prior to Cycle 1 Day 1. The dose is recalculated in subsequent cycles in the event of a weight change of ±10% or greater.

An End of Treatment (EOT) visit occurs approximately 3 weeks after the last dose of HCW9218; however refer to Section 6.6 for exceptions. The patient transitions to the study required follow-up for disease response (if discontinued treatment for a reason other than disease progression) and survival for 1 year from the 1st dose of HCW9218.

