### 6.3 Monitoring for Dose Limiting Toxicities and Excessive Toxicity

Toxicity and adverse events are classified and graded according to NCI's Common Terminology Criteria for Adverse Events V 5.0 (CTCAE) unless otherwise noted in Section 10.

Note during the fast-track dose escalation only (Stage 1, Step 1), patients also are monitored for the pre-defined treatment emergent events defined in Section 6.2.1.

**Dose Limiting Toxicity (DLT)** is defined as any of the following treatment emergent adverse events using the NCI Common Terminology Criteria for Adverse Events (CTCAE) Version 5.0 within the 21 days after the 1st dose of HCW9218:

DLT event	Exceptions:		
Any Grade 3 or Grade 4 febrile neutropenia Any Grade 3 thrombocytopenia with bleeding Any Grade 3 or higher non-hematologic adverse event	
 
Grade 4 lymphopenia hat resolves to Grade 1 or lower (or to Baseline or lower, if pre-existing Grade 2 or higher) within 7 days
 
Grade 4 leukopenia that resolves to Grade 1 or lower (or to Baseline or lower, if pre-existing Grade 2 or higher) within 7 days
 
Grade 3 nausea, vomiting and/or diarrhea that last < 72 hours
 
Grade 3 or higher electrolyte abnormality that lasts < 72 hours, is not clinically complicated, and resolves spontaneously or responds to conventional medical interventions
 
Isolated Grade 3 elevation of ALT and/or AST that resolves to Grade 1 or lower (or to Baseline or lower, if pre-existing Grade 2 or higher) within 7 days
 
Grade 3 amylase or lipase that is not associated with symptoms or clinical manifestations of pancreatitis
 
		
	
 
Grade 3 fatigue, not due to disease progression, that lasts < 1 week
 
		
Hy's Law case (i.e., alanine aminotransferase/ aspartate aminotransferase (ALT/AST) >3 x ULN in combination with total bilirubin level (TBL) > 2 x ULN in the absence of cholestatic injury (ALP < 2 x ULN (Ricart, 2017; FDA, 2009)) and no other cause identified) after excluding biliary tract obstruction and liver metastasis  Inability to receive Cycle 2 dosing due to treatment related toxicity	MORE - I WOR		

The Dose Limiting Toxicity (DLT) Observation Period is defined as 21 days after the first dose of HCW9218. The DLT period does not end until the patient is assessed on Cycle 2 Day 1 (+3 days) and the results of lab work drawn on Cycle 2 Day 1 (+3 days) confirms no new DLTs since the previous assessment.

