# 6.6 Duration of Study Treatment

A minimum of two treatment cycles is planned and HCW9218 may continue until disease progression unless any one of the following occurs sooner:

- Patient requests to discontinue treatment early if in agreement, follow-up would continue as in Section 6.7 unless the patient also withdraws consent.
- In the judgement of the treating Investigator and documented in the medical record, study treatment is no longer in the best interest of the participant.

An End of Treatment (EOT) visit occurs 3 weeks (±1 week) after the last dose of HCW9218 to confirm no ongoing side effects/toxicity. If ongoing toxicity at the EOT visit, it should be managed as medically appropriate and documented, it if meets the criteria for documenting as an AE be followed until resolution or stabilization.

In the situation where a patient's EOT visit falls outside of the visit window due to a prolonged period before the decision to discontinue treatment is made, the EOT related activities may be retrospectively abstracted from the medical record from around the time the EOT would have occurred and/or delayed until the next standard of care visit. Missing items / research samples will not be considered a deviation.

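### Section 6.1's stop for a ≥20% weight change cites a criterion that Section 6.6 lacks and is reached only after a second ≥10% change, so after the Cycle 2 Day 1 assessment equal losses can be handled differently

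*Combined protocol and SAP*

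**What the plan says.** Section 6.1 sets the dose from the Cycle 1 Day 1 weight (or one taken within the 14 days before) and handles later changes in two steps.

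- **First change.** If a later cycle's Day 1 weight differs by 10% or more from the weight used for Cycle 1, "In this situation, the HCW9218 dose is recalculated using the more recent weight". No 20% test appears at this step.
- **Second change.** "The new dose is used for subsequent HCW9218 injections, unless a ≥10% weight change occurs based on the newer weight". Two bullets follow. If the weight has come back to about its Cycle 1 level, the dose may be recalculated and treatment goes on. The other bullet begins "The 10% weight change represents a ≥20% weight change from the Cycle" 1 Day 1, calls this Grade 3, and describes it as "meeting the criteria for discontinuing treatment per" Section 6.6.

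Section 6.6 opens with "HCW9218 may continue until disease progression unless any one of the following occurs sooner" and lists two items: the patient's request, and the Investigator's documented judgement that "study treatment is no longer in the best interest of the participant". Toxicity appears there only as something to follow up at the End of Treatment visit.

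Two other places bear on the point. The Synopsis (Treatment Overview) says "Patients may continue until disease progression, unacceptable toxicity (an AE meeting the definition of a DLT") or for another reason given in Section 6.6. It also says, without qualification, that the dose is recalculated in later cycles when weight changes by 10% or more. Section 6.3 counts "Any Grade 3 or higher non-hematologic adverse event" as a DLT, with no exception for weight, within 21 days of the first dose.

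**The concern.** Section 6.1 states a numerical stop and gives its reason, which is that a 20% change is Grade 3. That reason does not depend on how many recalculations came before. As drafted, the stop has two defects. Its cross-reference leads to a list that does not contain it. It is also tested only when the latest step is itself at least 10% from the newer weight. Two patients with the same Grade 3 loss can then be treated differently while both comply with Section 6.1.

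What is at stake is whether a patient with that degree of weight change stays on the drug in a first-in-human study. Time on treatment also shapes the exposure behind the secondary objective on the safety and feasibility of repeat dosing. The documents do not allow that effect to be sized.

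**Working it through.** The plan gives no figure to reproduce. The check applies Section 6.1 literally to example weights.

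**Inputs from the plan.** First trigger: ≥10% from the Cycle 1 weight w0 (Section 6.1). Second trigger: ≥10% from the recalculation weight w1 (Section 6.1). Stop: ≥20% from w0, tested only once the second trigger has fired (Section 6.1). Dose Level 4: 1.2 mg/kg.

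**Assumption.** w0 = 80 kg. In paths 1 to 3 the 20% loss is reached after the Cycle 2 Day 1 assessment. All three end at 64 kg, and 64/80 - 1 = -20.0%.

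1. 80→71.5→64. First change 71.5/80 - 1 = -10.6%: recalculate. Second change 64/71.5 - 1 = -10.5%: the second trigger fires, the loss from w0 is 20%, **stop**.
2. 80→71→64. First change 71/80 - 1 = -11.25%: recalculate. Second change 64/71 - 1 = -9.9%: the second trigger does not fire and the 20% test is never reached, **continue**.
3. 80→64 in one step. First change -20.0%: Section 6.1 recalculates to 1.2 × 64 = 76.8 mg, **continue**.

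**Where the paths divide.** For a two-step loss the stop needs both w2 ≤ 0.8·w0 and w2 ≤ 0.9·w1. It fires at exactly 20% only if 0.9·w1 ≥ 0.8·w0, that is w1 ≥ 0.889·w0, or 71.1 kg here. A first recalculation at a loss between 10% and 11.1% leaves the stop at its stated threshold. Any larger first loss delays it.

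- In path 2 the delay is slight: 0.9 × 71 = 63.9 kg, or -20.1%.
- With a first recalculation at 15% loss (68 kg), the stop fires at 0.9 × 68 = 61.2 kg, or -23.5%. A patient going 80→68→62.4 has a second change of 62.4/68 - 1 = -8.2%. That patient continues at 62.4/80 - 1 = -22.0%.
- Gains behave the same way. For 80→88→96 kg the second change is 96/88 - 1 = +9.1%, so a 20% gain is not caught.

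**Does other text close the gap?** For a one-step change seen by Cycle 2 Day 1, yes. Section 6.1 calls it Grade 3, Section 6.3 makes it a DLT, and the Synopsis treats an event meeting the DLT definition as unacceptable toxicity. After that assessment the DLT definition no longer applies, while weight is still checked on each later cycle's Day 1. The opening line of Section 6.1 names unacceptable toxicity as a reason to stop but sets no threshold.

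**Frequency.** The documents give no rate of ≥20% weight change. Section 7.2 lists weight gain of unstated size at 4 to 20 per 100 for similar drugs. Weight loss is not listed there or in Appendix II. Neither source can be turned into a count of affected patients.

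**The case against.** The strongest reply is that no patient has to stay on treatment. A provider assesses the patient before every dose, dosing may be delayed for ongoing treatment-related toxicity, unacceptable toxicity is a general reason to stop, and the best-interest item in Section 6.6 permits stopping at any time. The intent is also readable, since the bullet itself says that a 20% change is Grade 3 and warrants stopping. All of this stands. It means that continued dosing is permitted, not required. It does not make the stated rule work at its stated threshold, and it turns a numerical stop into a matter of discretion for some patients and not others.

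Several stronger readings are tempting, but the documents do not support them.

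- A reader might infer that a one-step 20% loss at Cycle 2 Day 1 is simply re-dosed. The DLT definition and the Synopsis already cover it, so the one-step gap exists only later.
- A reader might infer that a second change of ≥10% that stays short of 20%, such as 80→72→64.8 kg (-10.0%, then -19.0% from Cycle 1), has no instruction. The Synopsis directs recalculation for any change of 10% or more.
- A reader might see harm in path 2's unchanged dose at Dose Level 4: 1.2 × 71 = 85.2 mg, and 85.2/64 = 1.331 mg/kg, 10.9% above 1.2. That is the plan's ordinary tolerance for changes under 10%, which the fix keeps.
- A reader might want an upper limit on how late the stop can fire. There is none, because Section 6.1 does not cap the first change.

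**Conclusion.** The point holds, at the low end of minor. Section 6.1 relies on a discontinuation criterion that Section 6.6 does not contain, and the order of its steps makes the 20% stop depend on the path taken. After the Cycle 2 Day 1 assessment, the same 20% loss leads to a stop on one path and to continued dosing, subject to the Investigator, on two others.

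This rests on a literal reading of Section 6.1 and on illustrative weights; the thresholds are the plan's own. The number of patients affected is unknown and may be zero. A reader might infer that dose finding is compromised. It is not, because the MTD and the DLT evaluation rest on the first 21 days and the Cycle 2 Day 1 assessment, which this does not touch.

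**What to change.** Replace the two bullets in Section 6.1 with one ordered check at every cycle's Day 1:

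1. If weight differs by ≥20% from the Cycle 1 Day 1 weight, discontinue HCW9218, whatever recalculations came before.
2. Otherwise, if weight differs by ≥10% from the weight used for the current dose, recalculate on the current weight and continue.

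Add to the list in Section 6.6: ≥20% weight change from Cycle 1 Day 1 (Section 6.1).

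Paths 1, 2 and 3 then all stop at 64 kg. The path 80→72→64.8 is recalculated to 1.2 × 64.8 = 77.8 mg. A patient who gains and returns (80→89→80, second change 80/89 - 1 = -10.1%) is recalculated to 1.2 × 80 = 96.0 mg. If the sponsor means the stop to be a judgement, Section 6.1 should say so and not present it as a criterion already met.

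The cost is a short edit to two sections at the next amendment. Day 1 weights are already recorded (Section 8.1), so no visits, data or patients are added. The downside is that an occasional patient whom the literal rule would have left on treatment is now stopped.

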# 6.1.1 Provider's Assessment Prior to Each HCW9218 and Dose Delay

In order to proceed with a planned HCW9218 injection, a provider must assess the patient prior to each HCW9218 dose to rule-out any of the following contraindications for dosing:

- the previous injection site reaction is not showing signs of resolving (improving) based on measurement or intensity
- signs or symptoms of a new infection
- fever > 101°F (38.3 °C)
- cardiac function by clinical exam and assessment of vitals for signs hypotension, arrhythmia, angina and myocardial infarction or symptoms of chest pain, murmurs, gallops, irregular rhythm, or palpitations with further assessment as clinically indicated.

The HCW9218 dose will be delayed for up to 1 week if one or more of the above conditions are present.

In addition, HCW9218 may be delayed for up to 1 week on the day of a planned dose for either of the following situations:

- Any ongoing treatment related toxicity.
- If in the opinion of the treating physician, holding HCW9218 would be of benefit to the patient.

